## **5.7 Dietary Restrictions**

Subjects should arrive following a minimum 10-hour fast to the clinic as described in the study design. All subjects will continue with their regular diet. Subjects will fast from the evening of Visit 3, Day 28, until the end of infusion. Water intake will be unrestricted.

Excessive caffeine use (i.e., more than five cups of caffeinated beverages per day) will not be allowed from Screening (Visit 0) through Visit 3. Excessive alcohol use or binge drinking will be discouraged during the study, and alcohol will be prohibited 72 hours prior to each visit. Subjects must refrain from smoking more than 10 cigarettes per day. Subject should not use any recreational or illicit drugs within one year prior to Screening through Visit 3.

Subjects will also be asked to refrain from any unusual or unaccustomed vigorous exercise during the course of the study.

## 6 STUDY PROCEDURES AND ASSESSMENTS

### 6.1 Safety Assessments

#### 6.1.1 Weight, Height and BMI

Weight, height and BMI will be measured at every visit ([Table 1](#)). The subject will be clothed while being weighed, but should remove shoes, coats, jewelry and other accessories. Height will be measured with the subject wearing no shoes.

#### 6.1.2 Vital Signs

Vital signs (including seated SBP/DBP and heart rate) will be recorded at all visits as described in [Table 1](#). Vital signs will be measured after the subject has been sitting for at least 5 minutes in a quiet environment and prior to any blood draw that occurs at the same time point. The recorded seated SBP/DBP value will be the mean of two measurements taken 2 minutes apart and always using the non-dominant arm.

#### 6.1.3 Physical Examination

A physical examination will be performed as described in [Table 1](#) or Early Withdrawal. The physical examination will include the following organ or body system assessments: skin; head, eyes, ears, nose, and throat; thyroid; lungs; cardiovascular; abdomen (liver, spleen); lymph nodes; and extremities, as well as an abbreviated neurological examination.

#### 6.1.4 12-Lead ECG

A 12-lead ECG will be performed at Screening ([Table 1](#)). The 12-lead ECG will be recorded after the subject has been resting at least 5 minutes in the supine position in a quiet environment. ECGs will be read for QT and QTc (Federicia's) intervals and clinically significant abnormalities.

#### 6.1.5 Clinical Laboratory Tests

Fasted blood and urine samples for clinical safety laboratory assessments will be collected and processed using standard procedures as indicated in [Table 1](#). Laboratory samples will be processed by appropriate laboratories.

In the event of abnormal clinical laboratory values, the Investigator will make a judgment whether or not the abnormality is clinically significant.

##### 6.1.5.1 Clinical Safety Labs

The clinical safety labs will include the following hematology, serum chemistry and urinalysis tests:

###### Hematology

- Hematocrit
- Hemoglobin
- Mean corpuscular hemoglobin
- Mean corpuscular hemoglobin concentration
- Mean corpuscular volume
- Platelet count

- Red blood cell distribution width
- Red blood cell count
- White blood cell count with differential

#### Serum Chemistry

- Sodium
- Potassium
- Chloride
- Bicarbonate
- ALT
- AST
- Gamma-glutamyltransferase (GGT)
- Total bilirubin
- Alkaline phosphatase
- Albumin
- Total Protein
- Blood urea nitrogen (BUN)
- Creatinine
- Uric acid
- Glucose
- Calcium
- Phosphorus
- Total cholesterol
- Triglycerides
- High-density lipoprotein cholesterol (HDLC)
- Low-density lipoprotein cholesterol (LDLC)

#### Urinalysis

- Appearance (color and character)
- Bilirubin
- Urobilinogen
- Protein
- Glucose
- Ketones
- Leukocyte esterase
- Urine blood
- Nitrite
- pH
- Specific gravity

#### 6.1.5.2 Pregnancy Test

A serum pregnancy test will be performed for women of child-bearing potential (WCBP) at Screening. A urine pregnancy test will be performed for WCBP at Visit 3 (Day 28) ([Table 1](#)).

### 6.1.5.3 Urine Drug Test

A urine drug test will be performed for drugs of abuse at Screening as indicated in [Table 1](#). These will include testing for amphetamines, barbiturates, cocaine metabolites, opiates, and benzodiazepines.

## 6.2 Efficacy Assessments

### 6.2.1 16-Hour Tracer Infusion

A 16-hour tracer infusion will be performed after 28 days of treatment. The blood draw schedule during the tracer infusion is documented in [Table 2](#) in [Section 3.7](#) of the protocol. Based on the blood draws the values for the following lab tests will be obtained:

- Endogenous Glucose Production (glucose that is produced by the liver which has the tracer attached),
- Key metabolites ( $\beta$ -hydroxybutyrate, acetoacetate, lactate, pyruvate, FFA, glycerol), and
- Key hormones (insulin, C-peptide, glucagon).

For each of the lab tests, the following parameters will be derived (as appropriate):

- $AUC_{(0-16)}$ ,
- $AUC_{(0-2)}$ ,  $AUC_{(0-4)}$ ,  $AUC_{(0-8)}$ ,  $AUC_{(0-12)}$ ,
- $AUC_{(2-16)}$ ,  $AUC_{(4-16)}$ ,  $AUC_{(8-16)}$ ,  $AUC_{(12-16)}$ ,
- $C_{max}$  (endogenous glucose production only),
- $T_{max}$  (endogenous glucose production only), and
- $T_{lag}$  (endogenous glucose production only).

### 6.2.2 Hemoglobin A1c (HbA1c)

Hemoglobin A1c will be collected at every visit.

### 6.2.3 Plasma Glucose Levels

Plasma glucose levels will be collected prior to dosing and after 28 days of dosing. The plasma glucose levels collected after the 16-hour infusion period is complete is the value that will be analyzed for this test.

### 6.2.4 Ketones and Free Fatty Acids

Ketones and free fatty acid levels will be collected prior to dosing and after 28 days of dosing. The values collected after the 16-hour infusion period is complete are the values that will be analyzed for these tests.

### 6.2.5 Lipids (Total Cholesterol, LDL Cholesterol, HDL Cholesterol and Triglycerides)

Lipids will be collected prior to dosing and after 28 days of dosing. The values collected after the 16-hour infusion period is complete are the values that will be analyzed for these tests.

## 7 ADVERSE EVENTS AND SAFETY REPORTING

### 7.1 Safety and Tolerability Assessments

Safety and tolerability will be assessed on an ongoing basis by review of reported AEs, physical examinations, 12-lead ECGs, weight, vital signs (SBP/DBP and heart rate) and clinical safety labs (hematology, serum chemistry and urinalysis).

### 7.2 Definition of Adverse Event

An adverse event (AE) is defined in 21 CFR 312.32(a) as follows:

Any untoward medical occurrence associated with the use of a drug in humans, whether or not considered drug related.

An AE can be any unfavorable and unintended sign (e.g., an abnormal laboratory finding), symptom, or disease during the course of the study, and does not imply any judgment about causality.

Treatment-emergent adverse events (TEAEs) are defined as any AE that starts or increases in severity after the first randomized dose of study treatment (active or placebo).

### 7.3 Definition of Serious Adverse Event

A SAE is defined in 21 CFR 312.32(a) as follows:

An AE is considered “serious” if, in the view of either the investigator or Sponsor, it results in any of the following outcomes:

- Death;
- Life-threatening AE;
- Inpatient hospitalization or prolongation of existing hospitalization;
- Persistent or significant incapacity or substantial disruption of the ability to conduct normal life functions;
- Congenital anomaly/birth defect.

Important medical events that may not result in death, be life-threatening, or require hospitalization may be considered serious when, based upon appropriate medical judgment, they may jeopardize the subject or subject and may require medical or surgical intervention to prevent one of the outcomes listed in this definition. Examples of such medical events include allergic bronchospasm requiring intensive treatment in an emergency room or at home, blood dyscrasias or convulsions that do not result in inpatient hospitalization, or the development of drug dependency or drug abuse.

An AE is considered “life-threatening” if, in the view of either the investigator or Sponsor, its occurrence places the subject or subject at immediate risk of death. It does not include an AE that, had it occurred in a more severe form, might have caused death.

## 7.4 Eliciting and Reporting of Adverse Events

AE monitoring will start immediately following the first dose of active treatment or placebo (Visit 1) and will continue through Visit 3. Any subject with a possible study treatment-related AE at the end of the study will be followed until resolution or stabilization of the event. Further, any SAE, whether or not related to study treatment that occurs within 30 days following the last dose of study treatment will be followed until resolution or stabilization of the event. This may require additional clinical assessments and laboratory tests. The follow-up results will be recorded in the subject's source documentation and in the eCRF.

Subjects will be instructed to report all AEs experienced during the study, and subjects will be assessed in clinic for the occurrence of AEs throughout the study. In order to avoid bias in eliciting AEs, subjects will be asked general, non-leading questions such as "How are you feeling?"

All AEs, including TEAEs, reported by the subject, observed or otherwise identified by the Investigator, or other Investigational Site personnel will be documented.

Medical conditions existing at Screening should be recorded as medical history. New or worsening pre-existing medical conditions or diseases are considered AEs if they arise or worsen after the Screening visit, and should be recorded as AEs.

Surgical procedures themselves are not AEs; they are therapeutic measures for conditions that require surgery. The condition for which the surgery is required is an AE if it occurs or is detected following the first dose of Study treatment Visit 1. Conditions leading to planned surgical procedures are not AEs if the condition(s) was (were) known before study treatment. In the latter case, the condition should be reported as medical history.

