
### 3 INVESTIGATIONAL PLAN

#### 3.1 Overall Study Design and Plan

This study is designed to explore the efficacy of ORMD-0801 compared to placebo on endogenous glucose production in subjects with type 2 diabetes (T2DM). Subjects will undergo an initial Screening Visit (Visit 0) to establish their eligibility to participate in the study. At Visit 1 (2 weeks after the Screening Visit), qualifying subjects will be randomized to either ORMD-0801 (8 mg) or matching placebo, study medication will be dispensed and subjects will dose, twice a day, once in the morning prior to breakfast and once at night prior to bedtime. Doses will occur at 45 minutes ( $\pm$  15 minutes) before breakfast and no later than 10 AM each morning, and at 8 PM ( $\pm$  120 minutes) each night, and no sooner than 1 hour after dinner. Subjects will return to the clinic, 2 weeks later, for Visit 2. At this visit, subject compliance will be assessed, medication will be dispensed, a blood sample will be collected to measure HbA1c and subjects will be questioned for any adverse events. Subjects will be scheduled to return to the clinic in 2 weeks for morning admission (8 AM  $\pm$  120 minutes) to the PK unit (Visit 3). Subjects will be provided with standardized meals and the morning dose in-clinic. A light standardized dinner meal will be provided at 6 PM  $\pm$  30 minutes. At approximately 8 PM ( $\pm$  60 minutes, and no sooner than 1 hour after dinner), subjects will be dosed with their study medication and will be started on a 16-hour infusion of [6,6-H2]-glucose tracer. Blood samples will be collected to measure endogenous glucose (tracer attached), plasma glucose, metabolites and hormones for the duration of the infusion. Blood samples will be drawn at baseline (pre-infusion), 45, 90, 120 and 150 minutes, and 3, 4, 5, 6, 7, 8, 9, 10, 11, 12, 13, 14, 15 and 16 hours (see [Table 2](#) for blood draw schedule). Subjects will be required to remain fasting from the evening of Day 28 until the end of the infusion. Water intake will be unrestricted. On Day 29, blood sample will also be collected to measure HbA1c. Following completion of the infusion, the subjects will receive a standardized lunch and will be observed for an additional 6 hours. Prior to discharge, a physical examination will be performed, and blood/urine samples will be collected for safety chemistry, hematology and urinalysis, following which subjects will be discharged from the CRU and will exit the study.

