1. A death within 30 days after study treatment administration where there is a reasonable possibility that the drug caused the event;
2. Two Grade 4 AEs where there is a reasonable possibility that the study treatment caused the events.

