## **5.3 Study Treatment Administration**

### **5.3.1.1 Double-Blind Treatment Administration**

All subjects will receive double-blind placebo or ORMD-0801 (8 mg insulin) twice a day, once in the morning and once in the evening, according to their randomization schedule from Visit 1 (Day 0) to Visit 3 (Day 28). Subjects will take one capsule (active or placebo), 45 minutes ( $\pm$  15 minutes) before breakfast and no later than 10 AM each morning, and one capsule at 8 PM ( $\pm$  120 minutes at Visits 1-2 and  $\pm$  60 minutes at Visit 3) each night, and no sooner than 1 hour after dinner.

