#### 7.4.2 Reporting of Serious Adverse Events, Including Death

The Sponsor will adhere to all expedited regulatory reporting requirements as per 21 CFR 312.32.

If an SAE, including death occurs during this study or within 30 days following the last dose of the study treatment, the Investigator must notify the Medical Monitor **within 24 hours** after becoming aware of the event.

Initial notification via the telephone does not replace the need for the Investigator to complete and sign the SAE form within the time frames outlined in the protocol. This timeframe also applies to additional new information (follow-up) on previously forwarded SAE reports. The contact information for the Medical Monitor is provided below.

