#### 7.4.2.1      Pregnancy Reporting

If the subject or partner of a subject participating in the study becomes pregnant during the study or within 30 days of discontinuing study medication, the Investigator should report the pregnancy to Integrium within 24 hours of being notified. Safety personnel will then forward the Exposure In Utero form to the Investigator for completion.

The subject or partner should be followed by the Investigator until completion of the pregnancy. If the pregnancy ends for any reason before the anticipated date, the Investigator should notify the Sponsor. At the completion of the pregnancy, the Investigator will document the outcome of the pregnancy. If the outcome of the pregnancy meets the criteria for immediate classification as an

SAE (i.e., postpartum complication, spontaneous abortion, stillbirth, neonatal death, or congenital anomaly), the Investigator should follow the procedures for reporting an SAE.

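### Deaths, SAEs and pregnancies count for up to 30 days after dosing, but no contact is scheduled beyond about 22 hours after the last dose

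*Combined protocol and SAP*

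**What the plan says.** **Provisions that reach 30 days**

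- Section 7.4.2 sets the investigator's 24-hour notification duty with the condition "If an SAE, including death occurs during this study or within 30 days following the last dose of the study treatment".
- Section 7.4 adds that "any SAE, whether or not related to study treatment that occurs within 30 days following the last dose of study treatment will be followed" until it resolves or stabilizes. Section 7.8 repeats this.
- Section 7.4.2.1 applies when a subject or a subject's partner "becomes pregnant during the study or within 30 days of discontinuing study medication".
- Section 4.3 halts enrollment and dosing temporarily if either of two criteria is met. The first is "A death within 30 days after study treatment administration where there is a reasonable possibility that the drug caused the event". The second, "Two Grade 4 AEs where there is a reasonable possibility that the study treatment caused the events", states no time limit.

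**What is scheduled**

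- Section 7.4: "AE monitoring will start immediately following the first dose of active treatment or placebo (Visit 1) and will continue through Visit 3".
- Sections 3.4.1 and 3.5.1: the last dose is the evening dose on Day 28, at about 8 PM. The 16-hour tracer infusion starts straight after it, and discharge comes after a further 6 hours of observation on Day 29.
- Section 3.1: final examinations and samples are taken, "following which subjects will be discharged from the CRU and will exit the study".
- Table 1 marks Day 29 as End of Study. The only column after it is Early Withdrawal.
- Section 3.6: a subject who withdraws early comes back the next day for a closing visit and is then discharged from the study.

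**The concern.** The sponsor chose 30 days as the period over which serious events and pregnancies matter, yet planned no contact over nearly all of that period. Section 7.4 asks subjects to report adverse events from the time they are in the study, and by the evening of Day 29 they have left it. The body of the protocol does not ask them to report anything afterwards.

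Two things are at stake. The first is completeness: if no late SAE or pregnancy is on record, the report cannot tell whether none occurred or none was volunteered. The second is the death criterion of the pausing rule, which can act only on a death that reaches the investigator. If enrollment is staggered (the documents give no timetable), other subjects could still be receiving study treatment while such a death goes unreported.

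**Working it through.** The documents give no coverage figure, so there is none to reproduce. The check is direct arithmetic on the visit schedule.

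**Inputs**

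- Last dose to start of infusion: 0 h (Section 3.4.1).
- Infusion: 16 h (Section 3.1). Appendix A gives 960 min, and 960 / 60 = 16 h.
- Observation after infusion: 6 h (Section 3.1).
- Window after last dose: 30 days (Sections 7.4, 7.4.2 and 7.4.2.1).

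**Coverage of the 30 days after the last dose**

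- Time from last dose to exit = 0 + 16 + 6 = 22 h. The infusion is tied to the dose, so the allowed ±60 minutes around 8 PM does not alter this.
- Window = 30 × 24 = 720 h.
- Covered = 22 / 720 = 3.1%.
- Not actively observed = 720 − 22 = 698 h, and 698 / 720 = 96.9%.
- Sensitivity to a later discharge: exit at 24 h gives 696 / 720 = 96.7%, and exit at 26 h gives 694 / 720 = 96.4%.

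**The death criterion is different.** Its 30 days run from administration, not expressly from the last dose. For a completer dosed from Day 0 to Day 28, it spans Day 0 to Day 28 + 30 = Day 58. Monitoring to Day 29 covers about 29 / 58 = 50% of that span. The 97% therefore describes only the part after the last dose.

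**Does other text supply the missing contact?**

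- Sections 7.4 and 7.8 follow subjects who have a possibly related event at the end of the study, and Section 7.9 follows significant findings at Visit 3. Both start from something already known at exit and cannot detect a new event.
- The 24-hour clocks in Sections 7.4.2 and 7.4.2.1 start when the investigator learns of the event. Nothing scheduled after exit brings that about.
- Section 4.3 promises efforts to reach subjects who miss follow-up appointments, but none is scheduled after Visit 3.
- The last scheduled pregnancy test is on Day 28 (Section 6.1.5.2). The early-withdrawal visit lists none, so a woman who withdraws before Day 28 has no scheduled test after Screening.

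**The case against.** The strongest reply is that the 30-day provisions are duties that begin once the investigator is aware of an event. They do not promise active surveillance. Soliciting adverse events to the last visit, while accepting reports of serious events for longer, is a coherent arrangement. This stands. A reader might infer that the protocol contradicts itself; it does not.

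Three further limits also stand:

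- A reader might infer that subjects have no contact at all after exit, or that the period is wholly unobserved. The follow-up of known events in Sections 7.4, 7.8 and 7.9 rules that out, and a late event that reaches the site must still be reported.
- A reader might infer that 97% of the pausing rule is blind. The Grade 4 criterion has no 30-day window, and the death criterion also covers the treatment period, when monitoring is active.
- The percentage measures clock time, not risk. The documents give no event rate for the period after exit.

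Nor do the documents show that the safety endpoint is compromised. Adverse events, including hypoglycemia, are elicited through Visit 3 and overnight in the unit after the last dose. Section 8.5.2 plans descriptive summaries only, and no planned table claims an absence of events over 30 days.

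Consent pages are not in the material reviewed, so subjects may be told there to report later events. Even so, detection would remain passive.

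**Conclusion.** The point holds as a gap in ascertainment. Following the plan as written, about 97% of the 30 days after the last dose (698 of 720 h, or 96.4% to 96.9% over the discharge times tried) has no active observation. New deaths, SAEs and pregnancies in that period depend on passive report. The figure assumes that the last dose is the Day 28 evening dose and that the subject leaves after the planned observation. For early withdrawals the share depends on when the last dose was taken, which the documents do not fix.

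The primary endpoint, measured during the infusion, is not touched. This is an inexpensive improvement to safety ascertainment and not a flaw that undermines the trial.

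**What to change.** - Schedule one telephone contact about 30 days after the last dose: about Day 58 for completers, and at the same interval after the last dose for early withdrawals. Limit it to survival, SAEs, pregnancy (including partners) and the outcome of adverse events ongoing at exit.
- Instruct subjects at discharge to report a serious event or a pregnancy for 30 days. The call mainly improves completeness: a death soon after exit could otherwise come to light up to about 29 days late (Day 58 − Day 29). The instruction gives the pausing rule a chance to act earlier.
- Amend Section 7.4 so that ascertainment of SAEs and pregnancies runs to the call, and add the call to Table 1. Align the wording on study exit in Sections 3.1 and 3.6.
- State that the cut-off for non-serious and treatment-emergent adverse events and for concomitant medication stays at Visit 3. The definition of treatment-emergent events in Section 7.2 has no end date, so without this statement minor events mentioned on the call could enter the tables.

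The cost is about 40 short calls, one eCRF page, and last-subject-out about 4 weeks later. If there is a single database lock, it moves by the same amount. If the sponsor declines the call, the protocol should at least say that detection after exit is passive and include the discharge instruction.

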### 7.4.1 Routine Reporting of Adverse Events

All AEs, whether or not associated with the study treatment, that are observed by the Investigator, other Investigational Site personnel, or those reported by the subject will be recorded in the subject's source documentation and on the AE page of the eCRF. Copies of the SAE eCRF pages or an SAE listing generated based on the eCRF pages will be submitted to the Sponsor at regularly scheduled intervals to allow the Sponsor to meet expedited regulatory reporting requirements under 21 CFR 312.32 (see [Section 7.4.2](#) for further detail) and regular regulatory reporting requirements under 21 CFR 312.33.

For each AE, the following information will be entered in the eCRF:

- Medical diagnosis of the event in standard medical terminology (if a medical diagnosis cannot be determined, a description of each sign or symptom characterizing the event);
- Date of onset of any new AE or worsening of a previously observed AE.
- Date of resolution of the event (or confirmation ongoing);
- Whether the event is serious (per definition in [Section 7.3](#)), and if so, the reason it is considered serious;
- Severity of AE (per definition in [Section 7.6](#));
- Assessment of the attributability of the AE to the study treatment [per definition in [Section 7.4](#)];
- Whether the event is expected (per definition in [Section 7.7](#));

- Action taken in treating the AE (including concomitant medications or therapies administered) and/or change in the study treatment administration or dose (including whether the study treatment was temporarily interrupted or discontinued);
- Outcome of AE (per definition in [Section 7.8](#)).

